6.4. Pooling of Centers

No pooling of centers is planned.

6.5. Subgroups

No subgroup analysis is planned.

6.6. Analysis Visit Window

Efficacy by-visit summaries will use the analysis visit. Unscheduled and early termination visits will be windowed based on the following analysis visit window. If multiple measurements are taken within the same window, the one taken closest to the target study day will be used for the analysis. If there are multiple measurements with same difference from target day, the later assessment should be used for the analysis.

		Visit	Window
Analysis Visit	Target Study Day	EASI, IGA, BSA, SCORAD	DLQI/cDLQI
Baseline	1	<=1	<=1
Week 1-2	10	2 to 19	NA
Week 4	29	20 to 42	NA
Week 8	57	43 to 71	NA
Week 12	85	72 to 99	NA
Week 16	113	100 to 141	100 to 141
Week 24 Follow-up	169	> 141	> 141

Daily diary efficacy data (pruritus and sleep disturbance NRS) will be classified into analysis visits as follows considering the data during the 7 days immediately preceding each scheduled visit.

This document is confidential.

SAP Version: Final Version 3.0, 21-Sep-2020

Controlled Document ID: 3903A.01, Effective Date 29-Oct-2018

Filing requirements: TMF

Sponsor: Galderma Research & Development, LLC; Protocol No.: RD.06.SPR.116912, Version 6.0

Analysis Visit	Target Study Day	Diary Data Window
Baseline	1	-7 to -1
Week 1-2	10	3 to 9
Week 4	29	22 to 28
Week 8	57	50 to 56
Week 12	85	78 to 84
Week 16	113	106 to 112
Week 24 Follow-up	169	162 to 168

Daily topical AD medication used data will be classified into visit intervals as follows.

Analysis Visit Interval	Target Study Day	Diary Data Window
Baseline to Week 1-2	10	1 to 9
Week 1-2 to Week 4	29	10 to 28
Week 4 to Week 8	57	29 to 56
Week 8 to Week 12	85	57 to 84
Week 12 to Week 16	113	85 to 112
Week 16 to Week 24 follow-up	169	113 to 168

Safety and pharmacokinetics data will not be windowed for by-visit summary. i.e., scheduled visit data will be used for analysis.

7. Demographic, Other Baseline Characteristics and Medication

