#### Notes:

- a Subjects are required to fast for at least 8 hours before the visit(s).
- b Visit 3 is a single visit occurring between Week 1 to Week 2.
- c For subjects that complete the Week 16 visit and will rollover to the nemolizumab LTE study, the Week 16 visit (Visit 7) will serve as the final study visit. See Section 7.6.1.
- A follow-up visit is required for subjects who discontinue after the Week 16 visit and will not rollover to the nemolizumab LTE study. The follow-up visit should occur 12 weeks after the last study drug injection. See Section 7.6.1.
- e Assessments to be conducted at the unscheduled visit(s) depend on the reason for the visit. See Section 7.6.2.
- Subjects who discontinue before the Week 16 visit should attend an early termination visit and a follow-up/final study visit 12 weeks after the last study drug injection. See Section 7.6.1.

CONFIDENTIAL Page 37 of 99

Galderma Research & Development, LLC Protocol Number: RD.06.SPR.116912 21-JUL-2020 Version 6.0

- g Patient-reported efficacy measurements (ACT and DLQI/cDLQI) should occur before investigator (efficacy and safety) assessments, blood sample collections, and study drug administration.
- h Peak and average pruritus NRS should be recorded by subjects once daily in the evening, beginning ≥ 2 weeks before Day 1.
- Sleep disturbance NRS should be recorded by subjects once daily in the morning, beginning ≥ 2 weeks before Day 1.
- Subjects will be asked to record the response (yes/no) to the following question each evening, "Did you apply the eczema medication your doctor gave you, to your skin today?", beginning ≥ 2 weeks before Day 1. See Section 7.5.8.1.1.
- Subjects with a history of asthma will complete the ACT at each study visit before physical examination and other investigator assessments. Subjects with de novo diagnosed asthma will complete the ACT beginning at the first visit of de novo diagnosis and at all follow-up study visits.
- Subjects aged 17 years or older will complete the DLQI, while subjects aged 12-16 years old will complete the cDLQI.

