## 8.1.5 Pruritus Numeric Rating Scale

Pruritus NRS is a scale to be used by the subjects to report the intensity of their pruritus (itch) during the last 24 hours (see Appendix 6). Pruritus NRS has been validated in other AD clinical trials in adults and the minimum clinically important difference was shown to be 3 to 4.

The screening PP NRS score, measuring maximal pruritus intensity, will be determined by	a single
PP NRS assessment (score ranging from 0 to 10)	

Subjects will receive instructions on how to use and record their pruritus NRS scores on an electronic device, and will complete the assessment once daily in the evening throughout the clinical trial (including the run-in and the follow-up period).

Subjects will be asked the following questions in their local language:

- For average itch intensity: "On a scale of 0 to 10, with 0 being 'no itch' and 10 being 'worst itch imaginable', how would you rate your itch
- For maximum itch intensity: "On a scale of 0 to 10, with 0 being 'no itch' and 10 being 'worst itch imaginable', how would you rate your itch at the worst moment

CONFIDENTIAL Page 56 of 99

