8.5. Pruritus Numeric Rating Scale

Subject-reported assessments of pruritus will be collected daily on a diary.

The Pruritus Numeric Rating Scale (NRS) will be used by the subjects to report the intensity of their pruritus (itch) during the last 24 hours. The scale for average itch intensity and maximum itch intensity has values in a range between 0 to 10, with 0 being 'no itch' and 10 being 'worst itch imaginable'.

Average and peak Pruritus NRS scores will be obtained based on the average and maximum daily scores during the 7 days immediately preceding each scheduled visit (rounding is not permitted), and will be denoted as "weekly" scores (average weekly and peak weekly, respectively). A minimum of 4 daily scores is required for these calculations, and if less than 4 daily scores are available the respective weekly score will be a missing value.

Weekly average of peak pruritus NRS and weekly average of average pruritus NRS scores will be summarized descriptively by visit as continuous variables using LOCF and OC. Absolute and percent changes from baseline will also be included in the analysis.

Absolute and percent change from baseline in weekly average of peak pruritus NRS and weekly average of average pruritus NRS using LOCF will be displayed graphically.

For the LOCF analysis, the imputation will be performed separately for each weekly average or peak pruritus NRS score.

All pruritus NRS data will be listed.

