8.6. Sleep Disturbance Numeric Rating Scale

Subject-reported assessments of sleep disturbance NRS will be collected daily on a diary.

Sleep disturbance NRS is a scale to be used by the subjects to report the degree of their sleep loss related to AD. The scale has values in a range between 0 to 10, with 0 being 'no sleep loss related to signs/symptoms of AD' and 10 being 'I cannot sleep at all due to the signs/symptoms of AD'.

Weekly sleep disturbance NRS scores will be obtained based on the average daily values during the 7 days immediately preceding each scheduled visit. A minimum of 4 daily scores is required for this calculation, and if less than 4 daily scores are available the respective weekly score will be a missing value.

Weekly average sleep disturbance NRS will be summarized descriptively by visit as continuous variables using LOCF and OC. Absolute and percent changes from baseline will also be included in the analysis.

Absolute and percent change from baseline in weekly average sleep disturbance NRS using LOCF will be displayed graphically.

For the LOCF analysis, the imputation will be performed for each weekly average sleep disturbance NRS score.

All sleep disturbance NRS data will be listed.

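### The fixed Day 106–112 diary window for Week 16 can turn a compliant subject's score into a missing value when the final visit falls 4 to 5 days early

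*SAP*

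**What the plan says.** SAP 6.6 assigns daily pruritus and sleep entries to analysis visits by "considering the data during the 7 days immediately preceding each scheduled visit". The table under that sentence gives fixed study days; for Week 16 the target is Day 113 and the window is Days 106–112.

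SAP 8.5 (pruritus) and 8.6 (sleep) repeat the seven-day description without fixed days. The pruritus section sets a floor: "A minimum of 4 daily scores is required for these calculations". It then says what happens when a subject falls short of that floor: "if less than 4 daily scores are available the respective weekly score will be a missing value". For sleep, "A minimum of 4 daily scores is required for this calculation".

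Under SAP 6.3, missing continuous efficacy values are filled by LOCF from post-baseline visits, with observed cases as the sensitivity analysis.

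Protocol 7.2 allows the Week 16 visit on Day 113 ± 5. Its notes say that, for subjects moving to the extension study, "the Week 16 visit (Visit 7) will serve as the final study visit". Protocol 8.1.5 says of the pruritus diary that subjects "will complete the assessment once daily in the evening throughout the clinical trial (including the run-in and the follow-up period"). The Protocol 7.2 notes add: "Sleep disturbance NRS should be recorded by subjects once daily in the morning".

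**The concern.** The text describes the week before a visit, while the table describes a calendar week. The two are the same only when the visit falls on its target day. No sentence says which one governs when it does not, so two programmers could derive different Week 16 scores from the same diary.

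The sharper problem arises when the diary ends at the Week 16 visit. A subject who attends early, within the permitted window, and has filled in the diary every day can still have too few entries on Days 106–112. The plan would then impute a score that it could have calculated. The same subject would keep an observed Week 16 EASI, IGA, BSA and SCORAD, because the SAP 6.6 window for those runs from Day 100 to Day 141.

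Change to Week 16 in peak pruritus, average pruritus and sleep disturbance are all listed secondary efficacy endpoints (SAP 4.4.3). With about 20 subjects enrolled, each affected subject is 1/20 = 5% of the sample.

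**Working it through.** **Inputs**
- Target day t = 113 and fixed window 106–112 (SAP 6.6).
- Permitted visit day v = 108 to 118 (Protocol 7.2, 113 ± 5).
- Minimum of 4 daily scores (SAP 8.5, 8.6).
- Assumption for the early-visit case: the diary stops at the Week 16 visit. The documents do not say this.

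**Reproducing the table.** t − 7 = 106 and t − 1 = 112. The same rule reproduces all six post-baseline windows: 3–9, 22–28, 50–56, 78–84, 106–112 and 162–168. The table is therefore the pre-visit week for a visit on its target day.

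**Formulas**
- Pre-visit week: v − 7 to v − 1.
- Fixed-window days before the visit: the smaller of 7 and v − 106. If the visit-day entry counts, add one, up to 7.
- Overlap of the fixed window with the pre-visit week: 7 − |v − 113|.

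| Visit day | Pre-visit week | Window days before visit | With visit-day entry | Score if diary stops at visit | Overlap |
|---|---|---|---|---|---|
| 108 | 101–107 | 2 | 3 | missing either way | 2 |
| 109 | 102–108 | 3 | 4 | missing, unless visit-day entry counts | 3 |
| 110 | 103–109 | 4 | 5 | available | 4 |
| 111 | 104–110 | 5 | 6 | available | 5 |
| 112 | 105–111 | 6 | 7 | available | 6 |
| 113 | 106–112 | 7 | 7 | available | 7 |
| 114 | 107–113 | 7 | 7 | available | 6 |
| 115 | 108–114 | 7 | 7 | available | 5 |
| 116 | 109–115 | 7 | 7 | available | 4 |
| 117 | 110–116 | 7 | 7 | available | 3 |
| 118 | 111–117 | 7 | 7 | available | 2 |

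The table assumes that no diary entry was skipped. On Day 110, without the visit-day entry, a single skipped day also takes the count below 4.

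**Early visit, diary stops.** On Day 108 or 109 the weekly score is missing, and LOCF takes an earlier one, normally Week 12 (Days 78–84). The diary for Days 101–107 or 102–108 may be complete. The sleep item is answered in the morning, so a visit-day entry is plausible for it. If that entry counts, only Day 108 fails for sleep.

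**Early visit, diary continues.** All 7 window days can be filled and the score exists. However, 113 − v of them fall on or after the visit: 5 for Day 108, down to 1 for Day 112.

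**Late visit.** The score exists, but its overlap with the actual pre-visit week falls from 6 days (Day 114) to 2 days (Day 118).

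**Other visits.** Baseline is unaffected because Day 1 is fixed. Weeks 1–2, 4 and 8 allow ± 3 days, so the overlap is at least 7 − 3 = 4. Weeks 12 and 24 allow ± 5 days, as Week 16 does.

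**The case against.** The strongest reply is that there is no contradiction. The text says *scheduled* visit, the table beneath it is organised by target study day, and every post-baseline window is the seven days before that target. Read as the nominal day, text and table agree, and a fixed calendar week is a legitimate definition because it holds time since first dose constant. This stands as a possible reading. It is not stated, though, and SAP 10.3 and 10.4 use the same term to separate planned attended visits from unscheduled ones. Even on the nominal reading, the SAP has no rule for a diary that ends before the window closes.

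Several stronger readings are tempting, and the documents do not support them:
- **Any early visit loses the score.** This fails for visits 1 to 3 days early, which can still reach 4 entries. It also fails for subjects who continue into follow-up, because the protocol has them keep recording.
- **The diary ends at Week 16 for rollover subjects.** This is an inference. The protocol says only that the visit is their final one, and SAP 3.3 allows up to 7 days between it and rollover.
- **A late visit scores the wrong week.** The fixed days all precede the visit, and they are the right week if the nominal week is intended.
- **Four of the 11 permitted visit days are affected.** This adds missing scores (Days 108, 109) to partial overlap (Days 117, 118). It is also not a probability, since no distribution of visit dates is given.
- **The diary week must match the concentration sampled at the visit.** SAP 9.4 drives the PK/PD models with each subject's predicted concentration time-course. Of the diary scores it names only weekly average peak pruritus, not sleep.

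The stakes are also limited. The observed-case analysis and the daily listings would expose an imputed value, and no sample size, power or decision rule depends on it.

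**Conclusion.** The point holds in a narrow form. The SAP does not say which anchor governs the weekly scores. In one foreseeable situation its fixed window discards usable data from a compliant subject who attended on time.

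That situation needs two things together: a Week 16 visit on Day 108 or 109, and a diary that stops at that visit. It leaves 2 or 3 eligible days, one more if the visit-day entry counts, against a minimum of 4. An earlier score, normally Week 12, then stands in for Week 16. For late visits there is a difference in definition, with 2 to 6 of 7 days in common, but no loss of data.

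How many subjects would be affected cannot be derived from the documents. The endpoints are secondary and descriptive, in a single-arm study whose primary endpoints are PK, immunogenicity and safety. The change is worth making because it is easy and keeps observed data from being imputed, but it does not threaten the study's main conclusions.

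**What to change.** State in SAP 6.6 whether the weekly diary windows are anchored to the target day or to the actual visit date.

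At minimum, add a rule for a diary that ends before Day 112 because an in-window Week 16 visit was the subject's final visit. In that case, calculate the Week 16 score from visit day − 7 to visit day − 1 and keep the 4-score minimum. A Day 108 visit would then use Days 101–107.

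A wider option is to anchor every attended visit to its actual date and keep the target-day windows only for missed visits. This would also match the wording of SAP 8.5 and 8.6, but choosing it over fixed windows throughout is partly a matter of preference.

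The cost is a few lines of SAP text and a date-based derivation, with no new data. The downside is that the calendar days labelled Week 16 vary between subjects, from Days 101–107 to Days 111–117 at the extremes if every attended visit is anchored to its actual date.

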# 9.4.3.3 Electrocardiogram

All ECG changes from screening at Week 16 and unscheduled visits will be summarized for safety reasons.

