6.1. General Methods

This section describes analytical analysis issues that relate to all or some of the analytic analysis sections that follow. It describes general guidelines for analysis as well as the following items:

- SAS version 9.4 or higher will be used.
- CCI will be responsible for reporting the demographic, safety, and efficacy data including listings of the administration information for collection of PK and PD samples.
- Unless otherwise specified, summaries will be presented by visit.
- The total number of subjects in the treatment group (N) will be used as the denominator for percentage calculations, unless stated otherwise in the table shell.
- Continuous variables will be summarized using the number of observations (n), mean, standard deviation (SD), median, minimum, and maximum. Categorical variables will be summarized using number of observations (n) and percentages of subjects.
- Subject data listings will be presented with the ITT population for efficacy assessments, with the Safety Population for safety assessments and with the PK population for PK assessments, unless stated otherwise.
- In general, the listings will be sorted by subject number, and assessment date (and time) if applicable.
- Multiple assessments at a given time point (repeat, and unscheduled) will not be included in summary tables unless specified otherwise, but will be included in the listings.

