All medications (prior and concomitant medications, rescue medications, and background TCS) will be listed on the ITT population.

8. Efficacy

All the efficacy analyses will be based on the ITT population. All efficacy variables will be summarized by visit from baseline unless specified otherwise. For efficacy analysis, unscheduled visit or ET visit data will be considered for by-visit summary.

All efficacy analysis will be performed using LOCF or Non-responder imputation (unless stated otherwise) and also performed with observed cases (OC) as sensitivity analysis (see Section 6.3 for more details). LOCF and Non-responder will be performed at all post-baseline visits up to Week 24.

In LOCF or Non-responder analyses, all efficacy data will be set to missing after rescue medication is used. In OC analyses, all data will be included even if subject has received rescue medication.

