10.5. ECG

A 12-lead Electrocardiogram (ECG) will be performed at Screening, Week 16, Unscheduled visit and Early Termination visits.

ECG scan will be reviewed centrally by the designated vendor .

The overall results of the ECGs recorded as 'Normal', 'Abnormal, not Clinically Significant (NCS)' or 'Abnormal, Clinically Significant (CS)' will be summarized by visit (scheduled visits only). And the shift table will be provided.

All 12-Lead ECG data will be listed.

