10.7. Respiratory Assessment - Spirometry/Peak Expiratory Flow

At screening, the investigator should specifically question all subjects about any medical history of asthma and their respiratory health (eg, wheezing, allergies and infections). All subjects will have spirometry/Peak Expiratory Flow (PEF) performed at screening and baseline. For subjects reporting a medical history of asthma, PEF will be performed at each visit during the clinical trial. For subjects diagnosed with de novo asthma, PEF will be performed at all visits starting with the visit in which the diagnosis was confirmed.

Actual PEF (L/min), Predicted PEF Rate (L/min) and Actual PEF Rate of the predicted value (%) will be summarized descriptively by visit (scheduled visit only) as continuous variables. Absolute change from baseline will also be included in the descriptive analysis.

Also spaghetti plots over time will be displayed graphically for Actual PEF (L/min).

Number of subjects with abnormal PEF (actual PEF < 80% of the predictive value) will be summarized separately.

PEF assessment will be presented in listings.

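### An ECG taken at early termination is listed but has no clear place in the ECG summary and shift tables; physical examination, PEF and ACT by-visit tables share the gap to a lesser degree

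*SAP*

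**What the plan says.** SAP 6.6 treats efficacy and safety differently. For efficacy: "Unscheduled and early termination visits will be windowed based on the following analysis visit window". The opening of SAP section 8 repeats this: "For efficacy analysis, unscheduled visit or ET visit data will be considered for by-visit summary". For safety, 6.6 says: "Safety and pharmacokinetics data will not be windowed for by-visit summary. i.e., scheduled visit data will be used for analysis". No safety section has a sentence that brings ET results into a by-visit table.

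The safety sections follow that rule. According to SAP 10.5 the ECG "will be performed at Screening, Week 16, Unscheduled visit and Early Termination visits", and its overall interpretation "will be summarized by visit (scheduled visits only). And the shift table will be provided". PEF values (10.7) "will be summarized descriptively by visit (scheduled visit only) as continuous variables". Physical examination (10.6) and ACT (10.8) carry the same restriction. SAP 6.1 adds a general rule: "Multiple assessments at a given time point (repeat, and unscheduled) will not be included in summary tables unless specified otherwise". It does not mention ET.

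The protocol schedule (7.2) collects ECG, physical examination, PEF, ACT, vital signs and laboratory samples at the ET visit. On ECG, protocol 9.4.3.3 says: "All ECG changes from screening at Week 16 and unscheduled visits will be summarized for safety reasons". SAP 4.3 defines the ECG endpoint at the same visits, and SAP section 14 declares no change from the protocol.

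**The concern.** ECG change from screening, physical examination, PEF and ACT are all primary safety endpoints (protocol 6.2.3, SAP 4.3). Subjects who leave early are a group in which a safety reviewer wants to see the last value on study. The protocol obtains that value, but for these four assessments the SAP does not say that it reaches a summary table. For ECG the whole post-dose contribution of an early leaver can depend on the ET recording, so its omission would remove the subject from the ECG tables. The PEF and ACT tables are also marked in SAP section 18 for both the interim analysis and the IDMC.

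**Working it through.** The plan gives no figure to reproduce: the study is not powered and no dropout rate is stated. The check is mainly a comparison of the sections.

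**1. Which assessments have a place for an ET value**

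| Assessment | By-visit table | Last post-baseline row | Other summary that might hold an ET value |
|---|---|---|---|
| ECG (SAP 10.5) | scheduled visits only | none | shift table, with no limit in its own sentence |
| Physical examination (10.6) | scheduled only, shift included | none | clinically significant respiratory findings, no limit stated |
| PEF (10.7) | scheduled only | none | count below 80% of predicted, no limit stated |
| ACT (10.8) | scheduled only | none | count at 19 or lower, no limit stated |
| Hematology, chemistry (10.3) | scheduled only | last, minimum, maximum in the treatment period | potentially clinically significant results |
| Urinalysis (10.3) | scheduled only | unclear: the row is described in the same bullet | potentially clinically significant results |
| Vital signs (10.4) | scheduled only | last in the treatment period | potentially clinically significant results |

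The first four rows lack a device that the SAP already uses elsewhere.

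**2. Why ECG is the main case**

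In protocol 7.2 the ECG is scheduled at screening and Week 16, plus ET and, where applicable, unscheduled visits. Week 24 has none. Notes to 7.2 send a subject who discontinues before Week 16 to an ET visit and a final visit 12 weeks after the last injection. That final visit repeats physical examination and, for subjects with asthma, PEF and ACT, but not ECG. If the subject does not attend Week 16, the ET ECG is the only planned post-dose ECG.

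**3. Who is affected for PEF and ACT**

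After baseline, PEF and ACT are done only in subjects with a history of asthma or newly diagnosed asthma (protocol 8.6.9). The affected number is therefore a subset of the early leavers.

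**4. Illustrative size (assumption)**

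For an early-termination rate d among 20 subjects, the expected number is 20 × d and the chance of at least one is 1 − (1 − d)^20.

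- d = 5%: 1 expected; 1 − 0.95^20 = 64%
- d = 10%: 2 expected; 1 − 0.90^20 = 88%
- d = 20%: 4 expected; 1 − 0.80^20 = 99%

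**5. Limit of the rows that do exist**

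SAP 6.2 ends the treatment period of a discontinued subject at the earlier of the ET date and 4 weeks after the last injection. For a last injection on Day 1, 29, 57 or 85, adding 28 gives Day 29, 57, 85 or 113. An ET result after that day also falls outside the existing treatment-period rows.

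**6. Unscheduled ECGs**

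Protocol 9.4.3.3 and SAP 4.3 include unscheduled ECGs. SAP 10.5 limits the summary to scheduled visits, and 6.1 excludes unscheduled results by default. SAP section 14 does not declare the difference.

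**The case against.** The strongest reply is that the exclusion is not proven. The SAP does not define a scheduled visit; ET is a column of the protocol schedule; the exclusion in 6.1 names repeat and unscheduled results, not ET; and in 10.5 the bracket sits in the sentence before the one on the shift table. The ECG and ACT endpoints do not name ET either. All of this is true, and it is why the point is stated as the natural reading. That reading is still the more likely one, because 6.6 and section 8 name ET explicitly where it is to be used.

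A reader might infer that early leavers' safety results never reach any summary, so that the tables describe only those who tolerated the drug. The documents do not support this. Adverse event tables cover the whole Safety Population. Clinically significant ECG, examination, laboratory and vital-sign changes become adverse events. In subjects with asthma, PEF below 80% of predicted is to be reported as an event of special interest. ECG, laboratory, PEF and ACT data and abnormal examinations are listed, and about 20 subjects can be read individually. Listing 16.2.8.2.12 shows subjects with a drop of at least 15% in PEF or ACT. Subjects who stop drug are encouraged to attend the remaining visits (protocol 7.4.4), so not every one of them lacks a Week 16 ECG.

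A reader might also add urinalysis, or the abnormal-PEF, ACT and respiratory-finding counts, to the list of omissions. The wording of 10.3 can be read to cover urinalysis, and the three counts state no scheduled-only limit.

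What these points leave standing is the ECG table. The adverse event route captures only changes judged clinically significant, whereas the shift table is meant to show movement across normal, abnormal not clinically significant and abnormal clinically significant.

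**Conclusion.** The point holds in a limited form. On the natural reading, an early leaver who does not attend Week 16 is absent from the post-dose ECG summary and shift although an ECG was taken at ET. The by-visit physical examination tables, and the continuous PEF and ACT tables for subjects with asthma, also omit ET values; there the loss is smaller, because earlier visits and the 12-week follow-up contribute. Urinalysis and the three separate counts are not clearly affected.

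The size cannot be derived from the documents. If 1 to 4 of 20 subjects leave early and do not return for Week 16, 1/20 = 5% to 4/20 = 20% of subjects would be missing from the post-dose ECG tables. The conclusion assumes that ET is not counted as a scheduled visit. The undeclared difference over unscheduled ECGs between SAP 10.5 and both SAP 4.3 and protocol 9.4.3.3 does not depend on that assumption.

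**What to change.** - In SAP 10.5 to 10.8, add a last post-baseline row that includes ET values for ECG, physical examination, PEF and ACT. For ECG, present the shift from screening to the last post-dose ECG.
- In SAP 6.6, 10.3 and 10.4, state that the existing last, minimum and maximum rows include ET results, whether they cover urinalysis, and how an ET result after the treatment-period cut-off in 6.2 is handled.
- Align SAP 10.5 with SAP 4.3 and protocol 9.4.3.3 on unscheduled ECGs, or declare the difference in section 14.

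Mapping ET safety results to the nearest visit with the efficacy windows is not recommended. It cannot help ECG: an ET ECG on Day 60 would fall in the Week 8 window (Days 43 to 71), where no ECG is scheduled.

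The cost is SAP wording and a little programming, with no new data. The small downside is that a last-value row mixes study days, as the existing laboratory and vital-sign rows already do.
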